11. DATA REPORTING / REGULATORY REQUIREMENTS

Adverse event lists, guidelines, and instructions for AE reporting can be found in Section 7.0 (Adverse Events: List and Reporting Requirements).

11.1 Data Reporting

11.1.1 Method

The DF/HCC Office of Data Quality (ODQ) will collect, manage, and perform quality checks on the data for this study.

11.1.2 Responsibility for Data Submission

Investigative sites are responsible for submitting data and/or data forms to the Office of Data Quality (ODQ) in accordance with DF/HCC policies.

11.2 Data Safety Monitoring

The DF/HCC Data and Safety Monitoring Board (DSMB) will review and monitor study progress, toxicity, safety and other data from this study. The Board is chaired by a medical oncologist from outside of DF/HCC and its membership composed of internal and external institutional representation. Information that raises any questions about participant safety or protocol performance will be addressed by the Sponsor-Investigator, statistician and study team. Should any major concerns arise, the DSMB will offer recommendations regarding whether or not to suspend the study.

The DSMB will meet twice a year to review accrual, toxicity, response and reporting information. Information to be provided to the DSMB may include: participant accrual; treatment regimen information; all adverse events and serious adverse events reported across all sites by category; summary of any deaths on study; audit results; and a summary provided by the study team. Other information (e.g. scans, laboratory values) will be provided upon request.

12. STATISTICAL METHODS

12.1 Study Design/Endpoints Sample Size and Power

We powered the study to detect clinically meaningful changes in the primary endpoint of M-protein and levels.⁶⁷⁻⁶⁹ To facilitate precise baseline calculations, we ascertained M-protein level data from a representative clinical sample of MGUS and SMM patients at Dana-Farber. Accordingly, assuming a standard deviation of 0.99 g/dL, a type I error rate of 0.05, 60 participants will provide 80% statistical power to detect a between group difference of 0.73 g/dL, and 90% power to detect a between group difference of 0.84 g/dL which are considered clinically meaningful changes.⁶⁹⁻⁷¹ Specifically, a change of 0.73 g/dL indicates that we are

powered to detect > a 10% change in M-protein within the 6-month intervention period. Notably, a 10% change is consistent with the definition of “evolving M-protein” concentrations by Ravi et al and others⁶⁸ and evolving M-protein concentrations of this magnitude are associated with a shorter time to progressing than patients with non-evolving disease. It is also notable that although this trial should have a minimal drop-out rate or MM-defining events (and need to initiate standard MM treatment) during the 6-month intervention period.

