3. PARTICIPANT SELECTION

3.1 Eligibility Criteria

3.1.1 Diagnosed with high-risk MGUS or low-risk SMM⁶³ defined below:

Higher-Risk MGUS: bone marrow plasma cell concentration <10%# AND either serum M-protein level ≥ 1.5 g/dL to <3 g/dL, abnormal free light-chain (FLC) ratio (<0.26 or >1.65), or IgA MGUS.

Note: individuals with an abnormal FLC ratio that are classified as light-chain only are eligible. Light-chain only patients are defined as complete loss of immunoglobulin heavy-chain, accompanied by abnormal FLC ratio with an increased level of the appropriate involved light-chain (increased kappa FLC in patient with ratio >1.65, and increased lambda FLC in patients with ratio <0.26).

Low-Risk Smoldering Myeloma: bone marrow plasma cells $\geq 10\%$ # with the absence of additional high-risk features, which are further defined in the exclusion criteria (3.2.1)⁶⁴

#A new bone marrow biopsy is preferred for plasma cell determination at screening; however, determination of eligibility can be made from most recent bone marrow biopsy performed as long as it was within 2 years of enrollment.

3.1.2 Absence of evidence of CRAB criteria* or new criteria of active MM or active WM which including the following (note if one or more criteria has not been evaluated (e.g., no MRI), the criteria for active MM or WM for that feature is considered unmet):

- Increased calcium levels (corrected serum calcium >0.25 mmol/dL above the upper limit of normal or >0.275 mmol/dL) related to MM
- Renal insufficiency (attributable to MM)

- Anemia (Hb 2g/dL below the lower limit of normal or <10g/dL) related to MM
- Bone lesions (lytic lesions or generalized osteoporosis with compression fractures)
- Bone marrow plasma cells $\geq 60\%$
- Serum involved/uninvolved FLC ratio ≥ 100 , provided the absolute level of the involved free light chain is at least 100 mg/L and repeated twice (light chain smoldering myeloma as described in section 2.4 is not an exclusion criteria).
- MRI with two or more focal lesion that is at least 5 mm or greater in size
- Hyperviscosity symptoms per WM guidelines for symptomatic WM

**Participants with CRAB criteria that are attributable to conditions other than the disease under study may be eligible*

3.1.3 At least 18 years of age.

3.1.4 Eastern Cooperative Oncology Group (ECOG) performance status of 0, 1, or 2.

3.1.5 The following laboratory values obtained prior to the first dose of study drug/placebo:

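### Section 12.1 presents a 0.73 g/dL detectable difference as power for a change above 10%, but 0.73 g/dL is 10% only at a baseline of 7.3 g/dL, and the plan gives no mean baseline

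*Combined protocol and SAP*

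**What the plan says.** Section 12.1 bases the calculation on local data: "we ascertained M-protein level data from a representative clinical sample of MGUS and SMM patients at Dana-Farber". It continues "assuming a standard deviation of 0.99 g/dL, a type I error rate of 0.05, 60 participants will provide 80% statistical power" for a difference of 0.73 g/dL, with 90% power for 0.84 g/dL, and says of these differences "which are considered clinically meaningful changes", citing references. It then glosses 0.73 g/dL as meaning that the trial is "powered to detect > a 10% change in M-protein within the 6-month intervention period", and adds "Notably, a 10% change is consistent with the definition of" an evolving M-protein pattern in the literature. Section 9.4.11 describes the differences that the trial is powered for as small.

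Section 12.1 gives no mean or median M-protein. It does not say whether 0.99 g/dL is an SD of levels or of 6-month change. Section 12.2 specifies a repeated-measures mixed model with baseline M-protein and disease subtype as covariates, but gives no baseline-to-6-month correlation and no detectable difference for that model.

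Section 3.1.1 sets one numeric M-protein range, for one MGUS route: "either serum M-protein level ≥ 1.5 g/dL to <3 g/dL". The alternatives, "abnormal free light-chain (FLC) ratio (<0.26 or >1.65), or IgA MGUS", carry no range, and neither does SMM. Light-chain-only patients are also eligible ("Light-chain only patients are defined as complete loss of immunoglobulin heavy-chain").

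**The concern.** A percentage power statement needs a baseline to divide by, and Section 12.1 has none. The sentence on evolving disease follows directly, so a reader will take 10% as roughly the effect the trial can detect. The stated calculation does not deliver that property.

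This matters most if the result is null. The primary result will be read against this paragraph, and the wording invites the inference that an effect of about 10% was ruled out. Whether the planned analysis could support that inference cannot be worked out from the plan.

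**Working it through.** **Inputs.** From Section 12.1: SD 0.99 g/dL, alpha 0.05, N = 60, differences 0.73 and 0.84 g/dL. From Section 5: 1:1 allocation, so 30 per arm. Sidedness is not stated. Two-sided is assumed because it reproduces the plan (one-sided gives 88.0% and 94.5%).

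**1. The plan's own figure.** Two-sample t-test, 58 degrees of freedom, no baseline adjustment.
- Standard error = 0.99 × √(2/30) = 0.256 g/dL.
- Noncentrality = 0.73/0.256 = 2.86 and 0.84/0.256 = 3.29.
- Power = 80.2% and 89.8%. Solving for the difference gives 0.728 g/dL (80%) and 0.843 g/dL (90%).

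The g/dL figures reproduce.

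**2. Baseline at which the difference equals 10%.** 0.73/0.10 = 7.3 g/dL, and 0.84/0.10 = 8.4 g/dL.

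**3. Illustration on the one numeric entry range.** The last column is the power of the step 1 test for a true 10% difference.

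| Baseline (g/dL) | 0.73 as share | 0.84 as share | 10% of baseline (g/dL) | Power for 10% if test SD is 0.99 |
|---|---|---|---|---|
| 1.5 | 48.7% | 56% | 0.15 | 8.9% |
| 2.0 | 36.5% | 42% | 0.20 | 12.0% |
| 3.0 | 24.3% | 28% | 0.30 | 21.1% |

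**4. Why that range cannot replace the missing mean.** The largest SD possible for values between 1.5 and 3 g/dL is (3 − 1.5)/2 = 0.75. If 0.99 is an SD of levels, the Dana-Farber sample must extend beyond that range.

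**5. The model in Section 12.2, if 0.99 is an SD of levels.** Approximate it by ANCOVA on baseline, ignoring disease subtype: adjusted SD = 0.99 × √(1 − ρ²), and 80% detectable difference ≈ 0.728 × √(1 − ρ²). The correlation ρ is an assumption; the documents give none.

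| Assumed ρ | Adjusted SD (g/dL) | 80% detectable difference (g/dL) | Share of 1.5 g/dL | Share of 3.0 g/dL |
|---|---|---|---|---|
| 0.5 | 0.857 | 0.63 | 42% | 21% |
| 0.7 | 0.707 | 0.52 | 35% | 17% |
| 0.8 | 0.594 | 0.44 | 29% | 15% |
| 0.9 | 0.432 | 0.32 | 21% | 11% |
| 0.95 | 0.309 | 0.23 | 15% | 8% |

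Simulated ANCOVA power at the last three differences was about 79 to 80%, so these values are approximate.

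**6. Correlation needed for 80% power at 10%.** Set 0.728 × √(1 − ρ²) equal to 10% of baseline b, so ρ = √(1 − (0.1b/0.728)²). This gives about 0.98 at b = 1.5, 0.95 at b = 2.25 and 0.91 at b = 3.0 g/dL.

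**The case against.** Nothing in Section 12.1 is numerically false. The power figures reproduce, and a difference of 0.73 g/dL is indeed more than 10% at any baseline below 7.3 g/dL. The section never claims 80% power for exactly 10%, and the sentence on evolving disease can be read as saying only that the detectable difference exceeds a prognostic threshold. Separate references support clinical meaningfulness. All of this stands. The point is not that 0.73 g/dL is unimportant, but that a statement equally true of a 15% or a 45% change tells the reader nothing about the detectable size, and 10% is the only figure offered.

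It is also fair that powering on an unadjusted comparison is generally conservative when the SD is of levels, so the analysis in Section 12.2 may do considerably better than Section 12.1 states. That stands too, but the plan does not use it to support the 10% figure and gives no correlation from which a reader could.

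The 24 to 49% share belongs to one entry route only. Patients entering by FLC ratio or IgA status may have lower values, which makes the share larger. For light-chain-only patients a percentage of serum M-protein may be undefined. SMM patients may exceed 3 g/dL, because under Section 3.2.1 a high M-protein alone does not exclude; that makes the share smaller. A reader might take 24 to 49% as the trial's detectable percentage, but the documents do not support that.

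**Conclusion.** The percentage claim in Section 12.1 does not follow from its calculation. What the calculation supports is 80% (90%) power for 0.73 (0.84) g/dL in an unadjusted two-sided comparison. Turning that into a percentage requires a mean baseline that is not given, and it would come to 10% only at 7.3 g/dL, a level that nothing in the eligibility criteria suggests as a mean.

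How far the planned analysis falls from 10% depends on what 0.99 g/dL describes. If it is the SD that enters the test, power for a true 10% difference is about 9 to 21% at baselines of 1.5 to 3 g/dL. If it is an SD of levels, as the reference to level data suggests, 10% may or may not be within reach, depending on the correlation.

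A reader might infer that the trial is underpowered, or that its power for a 10% change is 9 to 21%. Neither is shown. The stated power for 0.73 g/dL is right under its inputs, and the low figures hold only if the test SD is 0.99. Confidence is high that the inputs are missing and the gloss unsupported; no conclusion is drawn about the true detectable percentage.

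**What to change.** In Section 12.1:
- Replace the 10% gloss with 0.73 (0.84) g/dL as a percentage of the mean baseline in the Dana-Farber sample, among patients with measurable serum M-protein, and state that mean. Otherwise delete the percentage.
- Say whether 0.99 g/dL is an SD of levels or of 6-month change.
- If sensitivity near 10% is to be claimed, support it with the detectable difference of the model in Section 12.2. Use the correlation from the sponsor's own paired values about 6 months apart, or a stated range that includes lower values and is marked as an assumption and approximate.
- Keep the 10% benchmark sentence, and the word *small* in Section 9.4.11, only if the restated figure supports them.

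Possible wording, with the sponsor's figures for X, Y and Z: An unadjusted two-sided comparison of 30 per arm has 80% (90%) power for a difference of 0.73 (0.84) g/dL, which is X% (Y%) of the mean baseline of Z g/dL among sample patients with measurable serum M-protein.

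The cost is one paragraph and perhaps one word. The mean should come from data the sponsor has already gathered; paired values are needed only for the 10% claim. N = 60 and the analysis do not change. The downside is that the stated percentage may look less favourable.

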12.2 Statistical Analysis

The primary hypothesis being tested in this trial is that patients randomized to metformin will experience a significant reduction in M-protein levels compared to patients randomized to the placebo. This parameter has been selected as the primary endpoint because of its known clinical utility in predicting progression to overt MM in MGUS and SMM patients.⁶⁷⁻⁶⁹ Changes in this endpoint will be evaluated from baseline to follow-up in the two groups using a repeated measures mixed-effects model that accounts for the correlation between baseline and follow-up measures and is generally robust to missing data. The baseline value of the dependent variable (M-protein level) and disease subtype will be included as covariates in the regression models. Group-by-time interaction terms will be included as fixed-effects in the regression model. Model fit will be assessed using standard methods. Primary analysis of this endpoint will utilize stratified testing and intention-to-treat methods, using data from all participants randomized to an intervention group.⁷² Secondary/exploratory analyses will evaluate the influence of metformin on M-protein level in a per-protocol analysis.

A study project manager who is not involved in the statistical analysis will request information on treatment allocation from the DFCI Research Pharmacy. The Research Pharmacy is permitted to give the project manager information after the trial is closed to accrual and data collection on primary endpoints have been completed. However, all individuals performing the statistical analysis will remain blind to treatment group (metformin vs. placebo) for the primary outcome analysis.

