1. OBJECTIVES

1.1 Study Design

We will conduct a randomized placebo-controlled trial in patients with higher-risk monoclonal gammopathy of undetermined significance (MGUS) and low-risk smoldering multiple myeloma (SMM) to test the efficacy of metformin in reducing clinical indicators of disease progression in MGUS and SMM patients. The target enrollment of the trial is 60 patients. After informed consent is signed, participants will be randomized in equal numbers to metformin or its corresponding placebo. The treatment period for the trial is 6-months, with study assessments for the trial's primary outcome occurring at baseline and at the end of the 6-month treatment period. Participants will have the option to learn their treatment assignment after primary (6-month) outcome assessments are complete, and individuals randomized to metformin will have the opportunity to continue to take metformin for an additional 6-months to allow for the observation of potentially longer-term treatment response. Participants who choose to be unblinded and are taking placebo will discontinue study medication. Passive follow-up via medical record review will occur for up to 5 years post-randomization.

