10. STUDY CALENDAR

Registration and randomization should be conducted within 28 days (4 weeks) of baseline assessments. The 3-month safety labs should ideally be performed within 7 days of scheduled day 84 (preferably before). End of study/6- (or 12-) month assessment should ideally be completed within 7 days of last dose of study drug for those who completed 6 (or 12) months of treatment, or for those who were not able to complete 6 months of treatment, within 7 days of the 6 month timepoint or as close as feasible. Assessments must be performed prior to administration of any study agent and only after signing consent unless done as part of standard of care procedure. Each cycle is defined as 28 days.

	Screening/ Baseline	Day 1	Day 7	End of Cycle 1 (Day 28)	Day 48 (Optional)	End of Cycle 3 (Day 84)	End of Cycle 6 (Day 168)	End of Study Visit ¹⁰	Survival Follow Up ¹¹	EDC Timepoints
Metformin/Placebo ¹		-----Day 1-168-----								Day 1-168
Informed consent	X									N/A
Telephone Drug Adherence /AE Collection ²			X	X	(X)	X		X		N/A
Questionnaire/Survey ³	X							X		Baseline and EOT
Demographics	X									Baseline
Serum or Urine Pregnancy Test (if applicable)	X									Baseline
Medical history	X									Baseline
Physical exam ⁴	X				(X)			X		Baseline and EOT
Vital signs (BP, respiratory rate, temperature)	X							X		Baseline and EOT
Height	X									Baseline
Weight	X							X		Baseline and EOT
Performance status	X							X		Baseline and EOT
CBC w/diff, plts ⁵	X				X			X		Baseline and EOT
Serum chemistry ⁶	X				X			X		Baseline and EOT
Serum Free Light Chains (SFLC) Serum Protein Electrophoresis (SPEP), Immunofixation (SIFX), and Quantitative Immunoglobulins	X							X		Baseline and EOT
Research Bone Marrow Aspirate and Core ⁷	X							X		If a bone marrow biopsy or aspirate is performed at any time during the study as part of SOC, it should be captured in Inform
Research Blood Collection ⁸	X							X		N/A
Adverse Event Collection ⁹		From Time of Informed Consent to 30 days from Last Dose of Metformin								Record related AEs in database only

Survival and Event Collection ¹¹				X	N/A
1 Enough drug will be supplied for 3 cycles at a time. Labs will be reviewed prior to shipment of any medication. Participants may be shipped drug directly to their home following local policy, and will be instructed to return any unused drug, empty bottles, and completed diaries in pre-labeled return packaging to the lead site if they do not present in person to clinic.					

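### Baseline M-protein is both a repeated outcome and a covariate, so with complete data the group-by-time test is the unadjusted difference in mean change, with a standard error that depends on an unnamed covariance structure

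*Combined protocol and SAP*

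**What the plan says.** Section 12.2 evaluates change in M-protein "using a repeated measures mixed-effects model that accounts for the correlation between baseline and follow-up measures", so the baseline value is one of the modelled outcomes. It then states: "The baseline value of the dependent variable (M-protein level) and disease subtype will be included as covariates in the regression models". It continues: "Group-by-time interaction terms will be included as fixed-effects in the regression model". The section describes the model with the words "and is generally robust to missing data" and promises an intention-to-treat analysis "using data from all participants randomized to an intervention group".

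There are only two measurement times. Section 1.1 has assessments for the "primary outcome occurring at baseline and at the end of the 6-month treatment period". In the Section 10 calendar the row "Serum Free Light Chains (SFLC) Serum Protein Electrophoresis (SPEP), Immunofixation (SIFX), and Quantitative Immunoglobulins" is marked only at screening/baseline and at the end-of-study visit.

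Section 12.6 refers back to 12.2, and Section 12.7 prescribes the same model for continuous secondary outcomes. Neither 12.2 nor 12.7 names a covariance structure, a random effect, a baseline-by-time term, a tested contrast or a degrees-of-freedom method.

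**The concern.** Baseline can be handled in either of two sound ways: as a covariate for the 6-month value, or as an outcome with a constraint on the arms' baseline means. The plan does both at once. Reading the model as post-baseline only does not rescue it, because one follow-up value leaves nothing repeated and no time to interact with.

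A covariate that enters both visits with the same coefficient cancels from the change between them, so the stated adjustment does nothing for group-by-time. It also makes the baseline row partly a regression of a variable on itself, which distorts the residual variance. The primary p-value and confidence interval come from this model. Their validity would rest on a software choice made later.

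**Working it through.** **Inputs.** Sections 5 and 12.1: 60 patients, 1:1, so 30 per arm; SD 0.99 g/dL; alpha 0.05. Not in the documents, so assumed: equal SD at both visits, baseline-to-6-month correlation ρ from 0.5 to 0.95, and 0, 3 or 6 missing 6-month values.

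**Plan's own figure.** A two-sided two-sample t test with 30 per arm and SD 0.99 gives power 80.2% at 0.73 g/dL and 89.8% at 0.84 g/dL. The stated 80% and 90% reproduce. The difficulty is in the analysis model.

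**1. The contrast.** Let x be baseline, y the 6-month value and g the arm.
- Baseline row: x = a + γg + βx + e0
- Follow-up row: y = a + γg + τ + δg + βx + e1
- Difference: y − x = τ + δg + (e1 − e0)

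The baseline covariate (and likewise subtype) drops out of the difference. Any other combination of the two rows has its own free intercept and group term, so it tells us nothing about δ. With complete data, δ is estimated by the raw difference in mean change. In simulated trials the largest gap was 9e-16. In one data set at ρ = 0.8 both equalled −0.0908, while ANCOVA gave −0.1192.

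**2. Standard error, complete data, random intercept.** The baseline row has slope 1 on x and the follow-up row slope ρ, so the pooled slope is (1+ρ)/2. The residual variances are σ²(1−ρ)²/4 and σ²[(1−ρ)²/4 + 1−ρ²], with mean σ²(1−ρ)(3+ρ)/4. The residual covariance is −σ²(1−ρ)²/4. A random intercept cannot represent a negative covariance, so its variance tends to zero (in 99.9 / 93 / 77 / 60% of trials at ρ 0.5 / 0.8 / 0.9 / 0.95). In that case:
- model variance of δ = (4/30)·σ²(1−ρ)(3+ρ)/4
- true variance = 4σ²(1−ρ)/30
- SE ratio = √((3+ρ)/4) = 0.935 / 0.975 / 0.987 / 0.994

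In the ρ = 0.8 data set the SE was 0.1519 under a random intercept. It was 0.1550 under compound symmetry allowing negative covariance, equal to the change-score SE.

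**3. Unstructured covariance.** As the baseline coefficient approaches 1 the baseline row is fitted exactly. The restricted log-likelihood rose through 25, 56, 120, 184 and 249 as the baseline residual variance was set to 0.3, 0.1, 0.01, 0.001 and 0.0001. There is no maximum.

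**4. Missing 6-month values.** A patient with baseline only adds a row predicted by its own covariate. Take 3 missing per arm and ρ near 1, with five fixed effects (subtype left out):
- Residual variance is averaged over 114 − 5 = 109 degrees of freedom, where 2 × 52 = 104 are supported: 104/109 = 0.954. With complete data the counts are 116 and 115, so there is no shortfall.
- The model credits baseline means to 30 patients per arm, though only 27 inform change: (2/30 + 2/27)/(4/27) = 0.95.
- SE ratio ≈ √(0.954 × 0.95) = 0.95, close to the simulated 0.94.

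**5. Lost adjustment.** Variance of the change contrast over ANCOVA is 2(1−ρ)/(1−ρ²) = 2/(1+ρ). The chance baseline imbalance has SD 0.99·√(2/30) = 0.256 g/dL, of which the fraction (1−ρ) stays in the change contrast.

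**Results** (simulated under no effect; power rows excepted)

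| | ρ 0.5 | 0.8 | 0.9 | 0.95 |
|---|---|---|---|---|
| Complete, random intercept: SE ratio | 0.937 | 0.976 | 0.987 | 0.993 |
| – type I error, t (%) | 6.5 | 5.5 | 5.3 | 5.2 |
| – type I error, z (%) | 7.0 | 6.0 | 5.8 | 5.7 |
| 6 missing, random intercept: SE ratio | 0.90 | 0.94 | 0.94 | 0.94 |
| – type I error, t (%) | 7.8 | 6.5 | 6.5 | 6.6 |
| 3 missing, random intercept: type I error, t (%) | 6.9 | not run | 5.8 | 6.0 |
| 6 missing, compound symmetry: type I error, t (%) | 6.1 | not run | 6.2 | 6.5 |
| Variance, change / ANCOVA (formula) | 1.33 | 1.11 | 1.05 | 1.03 |
| Power with correct SE where ANCOVA has 79% (%) | 68 | 75 | 77.5 | 79 |
| Detectable at 80% power, change vs ANCOVA (g/dL) | 0.73 vs 0.63 | 0.46 vs 0.44 | 0.33 vs 0.32 | 0.23 vs 0.23 |
| Imbalance left in contrast (g/dL) | 0.128 | 0.051 | 0.026 | 0.013 |

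A correct SE gives 5.0% with t and 5.5% with z. Monte Carlo error is 0.05 points for complete data and 0.2–0.3 points with missing values. Repeat runs with 6 missing gave 6.2–7.9% for the random intercept, 5.6–6.2% for compound symmetry, and about 5% (up to 5.6%) for ANCOVA.

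**The case against.** Section 12.2 lists group-by-time among the fixed effects but never calls it the primary test, and it also mentions stratified testing. A model-based 6-month difference (group plus interaction) would be affected by the baseline covariate. This is true. But the section evaluates change from baseline in the two groups, so the interaction is the natural reading, and leaving the contrast unnamed is part of the defect.

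The identity is exact only with complete data and no baseline-by-time term. That also stands. With 6 values missing, though, the estimate still correlates 0.997 or more with the raw change difference among patients who have follow-up.

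The strongest objection is about size. At ρ = 0.5 the SD of 6-month change would be 0.99·√(2 × 0.5) = 0.99 g/dL, which is large for patients whose M-protein at MGUS entry is below 3 g/dL. A high ρ is more plausible, and there the complete-data error is negligible. Section 12.1 says that "this trial should have a minimal drop-out rate", and the 6-month assessment is sought even after treatment stops. A separate run of 4,000 trials at ρ 0.9 and 0.98 (Monte Carlo error about 0.35 points) found type I error of 4.7–5.3% with none or one missing and 5.5–6.1% with two or three. The harm is therefore modest if follow-up is nearly complete. It is not zero, and unlike the complete-data error it does not fade as ρ rises.

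A singular unstructured fit would announce itself through warnings. The plan promises a check of model fit but names no fallback.

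**Conclusion.** The concern holds. As written, and on the natural reading that group-by-time is the test, the primary analysis is a change-score comparison without the baseline adjustment the plan promises. It can be valid, mildly anti-conservative or not estimable, depending on an unstated covariance choice. The estimate itself is unbiased under randomisation.

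With complete data and ρ of 0.9 or more, the effect is slight: type I error 5.2–5.3% under a random intercept, and at most 5% in variance. At ρ = 0.5 it is 6.5% and 33%. With 6 of 60 follow-ups missing, type I error is about 6 to 8% under a random intercept and 5.6–6.5% under compound symmetry, across the whole range of ρ. These sizes rest on assumed ρ, assumed missing counts and normal data. The cancellation in step 1 depends on none of these, only on complete data and no baseline-by-time term.

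**What to change.** In Sections 12.2 and 12.7, replace the model with one of the following and say which is primary:

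- **ANCOVA** of the 6-month value on arm, baseline value and the randomisation strata in Section 12.4 (disease stage; heavy- or light-chain status). Patients without a 6-month value drop out, so the wording on analysing everyone randomised would need to match.
- **Constrained longitudinal model**, with baseline as outcome only, a common baseline mean across arms, an unstructured 2×2 covariance, the strata as covariates and no baseline covariate. This keeps every randomised patient who has a baseline value, so it fits the stated intention-to-treat aim better.

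In either case, state the tested contrast (adjusted 6-month difference with 95% CI) and the degrees-of-freedom method: residual for ANCOVA, Kenward-Roger for the longitudinal model. Disease stage is already a covariate in the plan; adding chain status and fixing the degrees of freedom complete the specification. The cost is SAP wording only, with no new data.
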